8.1.2.5 Reference Safety Information

The Reference Safety Information (RSI), in the current, approved IB, is a list of expected Serious Adverse Reactions which are classified using Preferred Terms according to the Medical Dictionary for Regulatory Activities (MedDRA). The RSI section will be used for assessing the expectedness of the study medication.

8.1.2.6 Pregnancy

Any pregnancy detected during the study, or that occurs within 30 days after stopping study medication, must be reported immediately to the Investigator. Pregnancy, in and of itself, is not regarded as an AE, unless there is suspicion that study medication may have interfered with the effectiveness of a contraceptive medication. If the patient becomes pregnant while on-study, the study drug should be immediately discontinued. Pregnancy information about a female patient or a female partner of a male patient should be reported immediately from the time the Investigator first becomes aware of a pregnancy or its outcome. This will be performed by the Investigator completing a Pregnancy Form and emailing it or faxing it to the Theradex Oncology Safety Desk (see Section [8.1.2.7](#)); contact the Theradex Oncology Safety Desk for the Pregnancy Form.

Any pregnancy complication, spontaneous abortion, elective termination of a pregnancy for medical reasons, outcome of stillbirth, congenital anomaly/birth defect, or SAE in the mother will be recorded as an SAE and will be reported as described in Section 8.1.2.7.

8.1.2.7 Reporting of Serious Adverse Events

AEs classified as serious require expeditious handling and reporting to Theradex Oncology to comply with regulatory requirements.

For any SAE that occurs while a patient is on-study; within 30 days of the last study drug administration, regardless of any opinion as to the relationship of the SAE to the study drug; or if any SAE that the Investigator feels is related to the study drug occurs later than 30 days after the last study drug administration, the Theradex Oncology Safety Desk must be notified immediately (within 24 hours of becoming aware of the event) by email, fax or telephone. Notification by email is preferred. The email address, fax and telephone numbers listed below may be used during both business and non-business hours. During non-business hours a recorded message will provide the telephone caller with the contact information for the on-call monitor.

All SAEs require that a Serious Adverse Event Report Form be completed and forwarded either via facsimile or as a PDF via email to Theradex Oncology at the fax number or email listed below within 24 hours of becoming aware of the event.

SAEs will be reported to: Theradex Oncology Safety Desk
[contact]
[contact]
Email: [contact]

8.1.2.8 Post-Infusion Observation Period

Observe/monitor for any signs and symptoms of IRRs, such as back pain, fever and/or shaking chills, flushing and/or itching, alterations in heart rate and blood pressure, dyspnea or chest discomfort, skin rashes, or anaphylaxis (e.g., generalized urticaria, angioedema, wheezing, hypotension, tachycardia, etc.).

During Part A of the study, each patient must remain in clinic for a minimum 6-hour safety observation period after each NBF-006 infusion until at least three patients at a specific dose level have been reviewed by the Safety Review Committee.

Reductions in the observation period at a given dose level may be recommended by the Safety Review Committee (consisting of Investigators, Theradex Oncology Medical Monitor, and Sponsor) after at least three patients have received a full cycle of treatment (defined as at least four doses and 2-week drug holiday) at that dose level.

Recommendations by the Safety Review Committee for a reduced observation period will be contingent upon:

- Absence of any significant safety concerns following a complete review of all clinical and laboratory data for all treated subjects at the given dose level and the preceding dose levels,
- Absence of any late-onset (>2 hours post-dose) IRRs or IRR symptoms that continue beyond 2 hours post-dose, and lack of any severe or serious IRRs,
- Review and consideration of cytokine and complement activation data at the given dose prior to making a recommendation to shorten the observation period.

If the Safety Review Committee recommends a reduced observation period, the minimum observation period allowed will be 2 hours following EOI from Cycle 2 onward during Part A of the study. Further reductions in the observation period may be suggested by the safety review committee as additional data has accumulated.

For Part B of the study, each patient must remain in clinic for a 6-hour safety observation period after the first dose, 2 hours after EOI for remaining doses in Cycle 1. The observation period may be further reduced to 30 minutes starting Cycle 2, after Medical Monitor and Investigator safety review. The observation period may be lengthened, if clinically indicated.

8.1.2.9 Management of Infusion-Related Reactions

The guidelines on dose modification and toxicity management for IRRs are outlined in [Table 5](#). All toxicities are graded according to NCI CTCAE Version 5.0.

Table 5: Dosing Modification and Toxicity Management Guidelines for Infusion-Related Reactions		
Severity Grade	Dose Interruption or Modification	Toxicity Management
Grade 1	The infusion should be temporarily interrupted and then resumed when symptoms are resolved.	
If symptoms have not resolved in 15 minutes:
 
 - Acetaminophen and/or antihistamines may be administered per institutional standard at the discretion of the investigator - Consider premedication prior to subsequent doses. - H1 antagonist (e.g., diphenhydramine, hydroxyzine, or chlorpheniramine) and an H2 antagonist (e.g., famotidine) dosed in accordance with approved labelling or the SOC before the start of investigational treatment administration (if premedication is administered parenterally, it should be given within 30 minutes of SOI; if premedication is given orally, it should be given 60-90 minutes prior to SOI). 
If the infusion reaction does not resolve within one hour after administration of acetaminophen and/or antihistamines the dosing should not be resumed the same day. Rechallenge should be discussed with the Medical Monitor, and premedication must be given if the patient receives any further doses.

Grade 2	The infusion should be temporarily interrupted and then resumed when symptoms are resolved.	
Grade 3/4	Permanently discontinue study drug/study regimen	
For Grade 3 or 4:
 
Manage severe IRRs per institutional standards (e.g., IM epinephrine, followed by IV antihistamines, and IV glucocorticoid)

8.1.2.10 Safety Data Review

The Medical Monitor will be responsible for ongoing safety data for the study. This will include a review of all AEs (serious and non-serious AEs) as they are reported by the study site.

Safety data will be reviewed periodically by a Safety Review Committee consisting of Theradex Oncology Medical Monitor, Sponsor, and Investigator. Details are provided in the Safety Plan. They will make decisions on dose modifications, cohort dose escalation,

transition to dose expansion phase (Part B), and may recommend changes to the post-infusion observation period.

8.1.2.11 Safety-Related Stopping Rules

If there is Grade 5 toxicity definitely, probably or possibly attributed to NBF-006 within 30 days of the last NBF-006 dose, the study may be temporarily or permanently stopped, pending a review by the Sponsor, Medical Monitor, and Investigators. During that time, no drug can be administered to any patient, until a decision is made.

8.2 Efficacy Assessments

Patients with measurable disease will be assessed at baseline and during the study by standard criteria. For the purpose of this study, patients should be reevaluated at the end of every even numbered cycle in Part A, dose levels 1-4 (0.15 mg/kg, 0.3 mg/kg, 0.6 mg/kg, 1.2 mg/kg), and at the end of every cycle for dose level 5 (1.6 mg/kg) in Part A and for all dose levels tested in Part B patients. In the event objective response (partial response [PR] or complete response [CR]) is noted, changes in tumor measurements must be confirmed by repeat assessments that should be performed at 4 weeks but no later than 5 weeks for patients in dose levels 1-4 in Part A after the criteria for response are first met. Response will be confirmed at 4 weeks or at the next scheduled scan (at Week 6 of the following cycle) for patients in dose level 5 in Part A and all patients in Part B. If a confirmative scan is done after 4 weeks, the next scheduled scan (at Week 6 of the following cycle) may be omitted. For stable disease (SD), follow-up measurements must meet the SD criteria at least 5 weeks after study entry.

8.2.1 Definitions

Response and progression will be evaluated in this study using the international criteria (version 1.1) proposed by the RECIST Committee.¹⁴ Changes in only the largest diameter (unidimensional measurement) of the tumor lesions are used in the RECIST 1.1 criteria. Note: Lesions are either measurable or non-measurable using the criteria provided below. The term “evaluable” in reference to measurability will not be used because it does not provide additional meaning or accuracy.

8.2.1.1 Measurable Disease

Measurable disease is defined by the presence of at least one measurable lesion. Measurable lesions are defined as those that can be accurately measured in at least one dimension [longest diameter (LD) in the plane of measurement to be recorded] with a minimum size of:

- 10 mm by computed tomography (CT) scan (CT scan slice thickness no greater than 5 mm)

- 10 mm caliper measurement by clinical exam (lesions which cannot be accurately measured with calipers should be recorded as non-measurable)
- 20 mm by chest x-ray

Malignant lymph nodes: To be considered pathologically enlarged and measurable, a lymph node must be ≥ 15 mm in short axis when assessed by CT scan (CT scan slice thickness no greater than 5 mm).

8.2.1.2 Non-measurable Disease

All other lesions (or sites of disease), including small lesions (LD < 10 mm or pathological lymph nodes with ≥ 10 to < 15 mm short axis) are considered non-measurable disease. Lesions considered truly non-measurable include: leptomeningeal disease, ascites, pleural/pericardial effusions, lymphangitis cutis/pulmonis, inflammatory breast disease, abdominal masses/abdominal organomegaly identified by physical exam and not followed by CT or magnetic resonance imaging (MRI).

Bone lesions, cystic lesions and lesions previously treated with local therapy must be considered as follows:

Bone lesions:

- Bone scan, positron emission tomography (PET) scan or plain films are not considered adequate imaging techniques to measure bone lesions. However, these techniques can be used to confirm the presence or disappearance of bone lesions.
- Lytic bone lesions or mixed lytic-blastic lesions, with identifiable soft tissue components, that can be evaluated by cross sectional imaging techniques (i.e., CT or MRI) can be considered as measurable lesions if the soft tissue component meets the definition of measurability described above.
- Blastic bone lesions are non-measurable.

Cystic lesions:

- Lesions that meet the criteria for radiographically defined simple cysts should not be considered malignant lesions (neither measurable or non-measurable) since they are, by definition, simple cysts.
- 'Cystic lesions' thought to represent cystic metastases can be considered measurable lesions, if they meet the definition of measurability described above. However, if non-cystic lesions are present in the same patient, these are preferred for selection as target lesions.

Lesions with prior local treatment:

- Tumor lesions situated in a previously irradiated area, or in an area subjected to other loco-regional therapy, are usually not considered measurable unless there has been demonstrated progression in the lesion.

8.2.1.3 Target Lesions

All measurable lesions up to a maximum of two lesions per organ and five lesions in total, representative of all involved organs, should be identified as target lesions and recorded and measured at baseline. Target lesions should be selected on the basis of their size (lesions with the LD) and their suitability for accurate repeated measurements (either by imaging techniques or clinically). A sum of the diameters (longest for non-nodal lesions, short axis for nodal lesions) for all target lesions will be calculated and reported as the baseline sum diameters. The baseline sum diameters will be used as reference by which to characterize the objective tumor response.

8.2.1.4 Lymph Node Assessment

For lymph nodes, measurements should be made of the short axis, which is defined as perpendicular to the LD of node assessed in the plane of measurement:

- Target lesion if short axis ≥ 15 mm
- Non-target lesion if short axis is ≥ 10 but < 15 mm
- Normal if short axis < 10 mm

For baseline, add the actual short axis measurement to the sum of LD of non-nodal lesions.

8.2.1.5 Non-target Lesions

All other lesions (or sites of disease) including pathological lymph nodes should be identified as non-target lesions and should also be recorded at baseline. Measurements of these lesions are not required and these lesions should be followed as “present”, “absent”, or in rare cases “unequivocal progression”. In addition, it is possible to record multiple non-target lesions involving the same organ as a single item on the eCRF (e.g., ‘multiple enlarged pelvic lymph nodes’ or ‘multiple liver metastases’).

8.2.1.6 Response Assessments After Palliative Radiotherapy

Palliative radiotherapy is allowed as medically indicated after completion of the first treatment cycle, and after discussion with medical monitor. Lesions assigned as targets at baseline should preferably not be included in the radiotherapy field, as it would preclude further response assessment per RECIST. Following palliative radiotherapy of RECIST target lesions, the irradiated lesion(s) and overall response assessment should be NA/Not evaluated, but remaining target and non-target lesions should continue to be monitored (an individualized schedule for radiology assessment is acceptable).

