8.2.3 Response Criteria

8.2.3.1 Evaluation of Target Lesions

- Complete Response (CR): Disappearance of all target lesions. Any pathological lymph nodes (whether target or non-target) must have reduction in short axis to < 10 mm.
- Partial Response (PR): At least a 30% decrease in the sum of diameters of target lesions, taking as reference the baseline sum diameters.
- Progressive Disease (PD): At least a 20% increase in the sum of diameters of target lesions, taking as reference the smallest sum on study (this includes the baseline sum if that is the smallest). In addition to the relative increase of 20%, the sum must also demonstrate an absolute increase of at least 5 mm. The appearance of one or more new lesions is also considered progression.
- Stable Disease (SD): Neither sufficient shrinkage to qualify for PR nor sufficient increase to qualify for PD, taking as reference the smallest sum diameters while on study.

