8.2.3.3 New Lesions

The finding of a new lesion should be unequivocal (i.e., not attributed to differences in scanning technique, change in imaging modality, or findings thought to represent something other than tumor, such as a ‘new’ healing bone lesion). A lesion identified on a follow-up study in an anatomical location that was not scanned at baseline is considered a new lesion and will indicate disease progression. If a new lesion is equivocal, continued therapy and

follow-up evaluation will clarify if it represents truly new disease. If repeat scans confirm this is definitely a new lesion, then progression should be declared using the date of the initial scan.

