8.2.3.4 Evaluation of Best Overall Response

The best overall response is the best response recorded from the start of the treatment until disease progression/recurrence (taking as reference for PD the smallest measurements recorded since the treatment started). The patient's best overall response assignment will depend on findings of both target and non-target disease and will also take into consideration the appearance of new lesions. Furthermore, depending on the nature of the study, it may also require confirmatory measurement. Specifically, in non-randomized trials where response is the primary endpoint, confirmation of PR or CR is needed to deem either one the "best overall response".

It is assumed that at each protocol-specified time point, a response assessment occurs. [Table 6](#) provides a summary of the overall response status calculation at each time point for patients who have measurable disease at baseline. When patients have non-measurable disease, [Table 7](#) should be used.

Table 6: Time point response: Patients with target (+/- non-target) disease

Target Lesions	Non-target Lesions	New Lesions	Overall Response
CR	CR	No	CR
CR	Non-CR / non-PD	No	PR
CR	Not evaluated	No	PR
PR	Non-PD or not all evaluated	No	PR
SD	Non-PD or not all evaluated	No	SD
Not all evaluated	Non-PD	No	NE
PD	Any	Yes or No	PD
Any	PD	Yes or No	PD
Any	Any	Yes	PD
CR=complete response, PR=partial response, SD=stable disease PD=progressive disease, NE=not evaluable			

Table 7: Time point response: Patients with non-target disease only

Non-target Lesions	New Lesions	Overall Response
CR	No	CR
Non-CR / non-PD	No	Non-CR / non-PD*
Not all evaluated	No	NE
Unequivocal PD	Yes or No	PD
Any	Yes	PD
CR=complete response; PD=progressive disease; NE=not evaluable * Non-CR/non-PD is preferred over SD for non-target disease		

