9.4.1 Duration of Overall Response

DOR is measured from the time of CR or PR (whichever is first recorded) until the first date that recurrent or progressive disease is objectively documented. Only patients with a confirmed CR or PR are included in the analysis. For a patient without evidence of PD, DOR will be censored.

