9.4.2 Duration of Stable Disease

Stable Disease is measured from the start of the treatment until the criteria for progression are met, taking as reference the smallest measurements recorded since the treatment started. Duration of stable disease will be analyzed in a similar method as DOR.

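### Section 8.2.1.6 codes overall response as not evaluated after target-lesion radiotherapy with no exception for progression, which conflicts with the PD rows of Table 6

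*Protocol*

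**What the plan says.** Section 8.2.1.6 permits palliative radiotherapy once the first cycle is complete. It prefers that target lesions stay outside the field, "as it would preclude further response assessment per RECIST". If a target lesion is irradiated, "the irradiated lesion(s) and overall response assessment should be NA/Not evaluated, but remaining target and non-target lesions should continue to be monitored". The rule has no end date, and it does not mention new lesions or progression.

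Section 8.2.3.4 sets the overall response at each visit through Table 6, on the premise that "It is assumed that at each protocol-specified time point, a response assessment occurs". For incompletely evaluated targets the table has one row: "Not all evaluated Non-PD No NE". Two further rows give PD for any target status: one when non-target disease has progressed, the other when a new lesion is present.

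The lesion-level definitions agree with Table 6. Section 8.2.3.1 says "The appearance of one or more new lesions is also considered progression", and section 8.2.3.2 repeats this for non-target disease. Section 8.2.3.3 adds "If repeat scans confirm this is definitely a new lesion, then progression should be declared using the date of the initial scan". None of these mentions radiotherapy.

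Section 9.2.1 lists duration of overall response and duration of stable disease among the Part B primary endpoints. Section 9.4.1 says "For a patient without evidence of PD, DOR will be censored", and section 9.4.2 says "Duration of stable disease will be analyzed in a similar method as DOR".

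**The concern.** Losing an irradiated target lesion makes the target sum unusable for judging shrinkage or stability, so withholding CR, PR and SD is reasonable. It does not make a new metastasis elsewhere unreadable. Section 8.2.1.6 keeps the remaining lesions under surveillance, yet as worded it offers no overall category for what that surveillance finds if the finding is progression.

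At stake is how progression dates are recorded for the two duration endpoints. Both end at progression or recurrence, and neither definition names another event, such as death, that would take the place of a progression left uncoded. Stopping treatment is not a dependable marker either, because section 4.5 lets patients continue after RECIST progression at the investigator's discretion. If observed progressions are entered as not evaluated and the analysis relies on that field, event times become censored times and the durations look longer.

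**Working it through.** No arithmetic applies, so the check sets the two rules side by side for a patient with an irradiated, non-evaluated target lesion.

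| Finding at the scan | Table 6 | 8.2.1.6 read literally | Agree? |
|---|---|---|---|
| Non-target disease not progressed, no new lesion | NE | Not evaluated | Yes |
| New lesion | PD | Not evaluated | No |
| Unequivocal non-target progression | PD | Not evaluated | No |
| Progression in the remaining target lesions | PD, if target status is classed as PD | Not evaluated | No, if so classed |

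The rules agree only in the first row. The second and third rows are plain conflicts. The fourth depends on how target status is classed when one target has been lost, which Table 6 does not spell out.

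An illustration on the Part B schedule, where scans fall at the end of each 6-week cycle:

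1. Week 6: SD. This is past the 5-week minimum for SD in section 8.2.4.1.
2. Week 8: a target lesion is irradiated. The first cycle is complete, so this is allowed.
3. Week 12: a new lesion is seen.
4. Under Table 6 and section 8.2.3.3, the overall response is PD, and duration of SD ends with an event at Week 12.
5. Under 8.2.1.6 taken literally, the overall response at Week 12 is not evaluated, and the site's response record holds no PD.

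The last step is whether that loses the event. Section 8.2.4.2 ends duration of response when progression is objectively documented, and section 8.2.4.3 ends duration of SD when the progression criteria are met. Neither refers to the overall-response field. An analyst working from lesion data could count Week 12 as an event; one working from the site's overall response could not. The protocol does not say which source governs.

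**The case against.** The strongest defence is that the sections can be read together. On that reading, the not-evaluated status concerns response judged from the lost target, as in Table 6's NE row, and the progression rules continue untouched. Section 8.2.1.6 says should rather than must and never mentions progression. Section 8.2.3.3 tells the site to declare progression for a definite new lesion. Censoring in section 9.4.1 is for patients without evidence of PD, and a documented new lesion is such evidence.

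Much of this stands. A reader might infer that PD is barred after target irradiation, or that the plan prescribes censoring an observed progression. The documents support neither: the first draws a prohibition from an unqualified instruction, and the second overlooks the duration definitions. What the defence does not remove is that 8.2.1.6 names the overall response itself, without qualification, so two careful readers could code one scan differently. The SAP may settle how durations are derived, but sites complete the response assessment from the protocol.

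A reader might also infer that radiation effects on non-target lesions could create responders. They could not. Overall CR in Table 6 requires target CR, and such a patient with persisting non-target disease is already PR. Disappearance of an irradiated non-target lesion could at most move PR to CR, and only with tumour-marker normalisation and confirmation.

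Finally, the analyses are descriptive with no sample-size calculation, and duration of response includes only confirmed responders. Both points limit the consequence.

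**Conclusion.** The inconsistency is real. After target-lesion radiotherapy, section 8.2.1.6 and Table 6 give different overall responses for a new lesion or unequivocal non-target progression, and sections 8.2.3.1 to 8.2.3.3 side with Table 6. The likely effect of following 8.2.1.6 literally is that some progressions are entered as not evaluated and may then drop out of duration of response or duration of SD.

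The size cannot be computed, because the protocol gives no expected frequency of palliative radiotherapy and no proportion of it that would involve target lesions. An affected patient must have a target lesion irradiated after Cycle 1, which the protocol discourages, and must later progress while still being scanned. The number is therefore probably small. The conclusion assumes that some sites would apply 8.2.1.6 as written and that the analysis may draw on the site's overall response. Because named Part B primary endpoints depend on the coding and the trial is open-label, it is worth settling before the data are examined.

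**What to change.** Reconcile the sections by adding one sentence to 8.2.1.6: after irradiation of a target lesion, CR, PR and SD can no longer be newly assigned and the overall response is NE, except that Table 6's PD rows continue to apply and any PD is recorded on the date of the scan that shows it. The sentence should make clear whether progression judged from the remaining target lesions is included. Put the same instruction in the eCRF guidance.

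Optionally, add that disappearance of an irradiated non-target lesion does not upgrade PR to CR.

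The cost is the sentence and the eCRF instruction. Section 8.2.1.6 already requires continued monitoring, so no scans are added, and the rules on giving radiotherapy are untouched. The one downside is that the reported durations may become slightly shorter.
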